## 9.3 POPULATIONS FOR ANALYSES

The Intention-to-Treat (ITT) Analysis Dataset inclusive of all participants will be included in the analysis. This is inclusive of all safety endpoints and encompasses the safety analysis dataset. Patients lost to follow-up will not be included in planned analyses.

## 9.4 STATISTICAL ANALYSES

### 9.4.1 GENERAL APPROACH

All patients will be enrolled in the study with hospital IRB approval after consent. Preliminary data collected will include clinical history and demographic data. Descriptive statistics on patients' demographic characteristics and echocardiographic parameters will be reported as means and standard deviations for continuous variables and frequency counts for categorical variables.

---

#### 9.4.2 ANALYSIS OF THE PRIMARY ENDPOINT

*For primary endpoints:*

Prevalence rates of cardiac death and myocardial infarction will be determined for the sample. The binomial test will be conducted to test the significance of deviations from the expected distribution of observations dichotomized as “*did not occur*” or as “*occurrence*” for each outcome.

*For safety endpoints:*

Prevalence rates for safety outcomes including ischemia-driven (ID) target lesion revascularization, ID target vessel revascularization, target lesion failure, target vessel failure, all-cause death, and myocardial infarction will be evaluated with binomial tests.

The test formula to be used is as follows:

$$P(X) = C^n_k \ p^k (1-p)^{n-k}$$

All data will be screened for non-parametric statistical test assumptions. Accordingly, all dichotomous outcomes will be screened for exclusivity and appropriateness for inclusion in data analysis. Missing data, nonadherence and data lost to follow-up will be excluded from the final analysis.

The a priori alpha level for all statistical tests will be set at .05. To adjust for a potentially inflated family-wise error rate, the Bonferroni correction ( $\alpha/m$ ) will be applied for multiple tests with the same sample.

---

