**Secondary Endpoints**

- Rate of cardiac death or myocardial infarction (SCAI definition) from 1 to 13 months post-index procedure in the overall enrolled “intent-to-treat” patient population
- Rate of Academic Research Consortium (ARC) definite/probable stent thrombosis (ST) involving SYNERGY™Stents from 1 to 13 months post-index procedure
- Rate of major bleeding (GUSTO severe/life threatening + moderate) from 1 to 13 months post-index procedure
- Ischemia-Driven (ID) Target Lesion Revascularization,
- ID Target Vessel Revascularization,
- Target Lesion Failure,
- Target Vessel Failure,
- All-Cause Death, and
- All-Cause Death or MI.

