## 9 STATISTICAL CONSIDERATIONS

### 9.1 STATISTICAL HYPOTHESES

Outcome measures include 1-13 month post-procedure rates of cardiac death and myocardial infarction. This single-arm prospective design will compare rates on the dependent variables following

Boston Scientific IVUS-guided SYNERGY™ Stent implantations with standard of care rates in the target population. The null and alternative hypotheses are as follows:

$$H_0 = p = p_0$$

The null hypothesis states that there is no difference on myocardial infarction or cardiac death rates.

$$H_1: p < p_0$$

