## 9.2 THE ALTERNATIVE HYPOTHESIS STATES THAT PATIENTS UNDERGOING SYNIVUS-DAPT TREATMENT WILL HAVE LOWER RATES OF MYOCARDIAL INFARCTION OR CARDIAC DEATH. SAMPLE SIZE DETERMINATION

An a priori power analysis was conducted for a one-sample binomial test with an alpha of .05 (one-tailed), beta of .05, constant proportion ( $p$ ) of .031, and assumed primary endpoint proportion of 0.0047 resulting in a needed sample size of 231.

The consideration of historical data on timing and incidence of myocardial infarction and stent thrombosis from published meta-analysis and related literature, the SCAAR registry and ACS subsets (De Luca, Dirksen, Spaulding, et al, 2012; Ellis, Colombo, Grube, et al, 2007; Palmerini, Biondi-Zocca, Riva, et al, 2012; Palmerini, Kirtane, Serruys, et al, 2012; SCAAR registry and ACS subset, 2016). Historic rates at 1-year follow up for ST showed variability ranging from 0.3 to 5.3%. Rates of MI range from 1.9 to 8.8%. A time-to-event bivariate exponential distribution function was used to determine criteria for sample sizes based on a 95% power determination resulting in a historic rate determination of 3.1%. Patients lost to follow-up will not be included in the final analysis, and additional patients will be recruited for study participation to reach the needed sample of 231.

The FDA has approved an initial phase of the investigation for 100 U.S patients. Accordingly, the sample size of N=100 for the initial phase is not statically based. Should approvals for study continuation be granted, the total sample size for subsequent phases will remain at 231, inclusive of subjects enrolled on this initial phase.

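### Section 9.4.2 applies Bonferroni with no m and no exemption for the primary composite, so success at N=231 means 2 or fewer events on one reading and 1 or fewer on another

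*Combined protocol and SAP*

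**What the plan says.** Sections 1.1 and 3 give a single primary endpoint: the composite of cardiac death or MI from 1 to 13 months. Section 9.2 sizes the trial on one test of one proportion, a "one-sample binomial test with an alpha of .05 (one-tailed), beta of .05, constant proportion" of .031 and an assumed endpoint proportion of .0047, which gives 231. Section 9.4.4 monitors the same composite and sets levels of .0054 at the interim and .0492 at the final analysis.

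Section 9.4.2 is worded differently. Its title is singular, but the sub-heading speaks of primary endpoints in the plural, and the text reads "Prevalence rates of cardiac death and myocardial infarction will be determined for the sample". It continues: "The binomial test will be conducted to test the significance of deviations from the expected distribution of observations dichotomized as" not occurring or occurring, and this is to be done for each outcome. Section 9.1 is similarly loose ("Outcome measures include 1-13 month post-procedure rates of cardiac death and myocardial infarction"), although it sets only one p against one p0.

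Section 9.4.2 then turns to safety: "Prevalence rates for safety outcomes including ischemia-driven (ID) target lesion revascularization" and five further named outcomes are also to have binomial tests. It fixes .05 for every test and says that the Bonferroni correction (alpha/m) "will be applied for multiple tests with the same sample". It gives no value for m, no list of the family and no exemption for the primary.

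Sections 1.1 and 3 list nine secondary endpoints. Two of them are missing from 9.4.2: definite/probable stent thrombosis, and "Rate of major bleeding (GUSTO severe/life threatening + moderate) from 1 to 13 months post-index procedure".

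**The concern.** The sample size and the final-look level assume that the composite is tested once at about .05. Read literally, the multiplicity sentence in 9.4.2 covers that test too and divides its alpha by an unstated number. The plan would then deliver neither the decision rule nor the power in 9.2.

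The expected number of events is very small (231 × .0047 = 1.1 under the assumed rate), so one event more or less in the rule matters. If m is settled only after the data are in, the choice of reading could decide whether the trial succeeded. A pilot described as hypothesis-generating still needs one rule once it states hypotheses, a power calculation and group-sequential levels.

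**Working it through.** **Inputs.** From 9.2: p0 = .031, p1 = .0047, one-sided alpha .05, power 95%, N = 231. From 9.4.4: final level .0492. From 9.4.2: the binomial formula and alpha/m. From Sections 1.1 and 3: one primary and nine secondary endpoints.

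**The plan's own figure.** Two large-sample formulas come close to 231.
- Arcsine: h = 2·asin(√.031) − 2·asin(√.0047), n = [(1.645 + 1.645)/h]² = 230.3, so 231. Power at 231 is 95.0%.
- Normal: n = [(1.645·√(.031×.969) + 1.645·√(.0047×.9953))/(.031 − .0047)]² = 228.5, so 229. Power at 231 is 95.3%.

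The 231 and the 95% therefore reproduce, but under approximations.

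**Exact test at N = 231.** P(X ≤ k) = Σ C(231, x) pˣ (1 − p)^(231 − x), summed over x = 0 to k.

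| k | P(X ≤ k), p0 = .031 | P(X ≤ k), p1 = .0047 |
|---|---|---|
| 0 | .00069 | .3368 |
| 1 | .00582 | .7042 |
| 2 | .02466 | .9037 |
| 3 | .07068 | .9756 |

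Success is declared for the largest k whose middle-column value does not exceed the level used. The last column is then the power.

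**Possible values of m.** The composite plus the six safety outcomes named in 9.4.2 gives 7. Taking the primary plus all nine secondary endpoints gives 10, or 9 if the intention-to-treat version of the composite is counted as a different sample.

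| Reading | Level | Rule | Power |
|---|---|---|---|
| Composite exempt | .05 or .0492 | ≤ 2 events | 90.4% |
| m = 2 from .05 | .0250 | ≤ 2 | 90.4% |
| m = 2 from .0492 | .0246 | ≤ 1 | 70.4% |
| m = 7 (9.4.2 list) | .00714 or .00703 | ≤ 1 | 70.4% |
| m = 9 | .00556 or .00547 | 0 | 33.7% |
| m = 10 | .00500 or .00492 | 0 | 33.7% |

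The m = 2 rows differ because .02466 lies between .0246 and .0250. The 1-event rule holds for m = 3 to 8 from .05 (.05/8 = .00625) and for m = 2 to 8 from .0492 (.0492/8 = .00615), since .00582 is below both. It fails at m = 9.

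**How often the reading matters.** Under p1, the chance of exactly 2 events is .9037 − .7042 = .1995. In about one trial in five, the exempt rule would declare success and the family-of-seven rule would not.

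**The case against.** The best defence is that the intent is clear. Sections 1.1 and 3 each name one composite primary, 9.2 sizes one test at an undivided .05, and 9.4.4 gives a specific final level for that composite. A specific level for a named endpoint may be taken to prevail over a general sentence on multiple tests, and the rule is then 2 or fewer events. This stands as to intent. It does not close the gap: 9.4.4 adjusts for repeated looks, 9.4.2 adjusts for several outcomes, and no section says that one displaces the other.

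Three stronger readings are tempting, and the documents do not support them.
- *Cardiac death and MI are two separate primary endpoints.* The wording of 9.4.2 could suggest this, but no null rate is given for either component and every other section uses the composite. It is a loose mismatch, not a rival definition.
- *The plan requires zero events.* That needs m of 9 or more, which means adding Section 3 endpoints that 9.4.2 does not say will be tested. The open word *including* leaves the possibility; it does not establish it.
- *The trial cannot succeed at 100 patients.* With 100 patients the smallest p-value is .969¹⁰⁰ = .0429, so any m of 2 or more would rule out rejection. But 9.2 says "Accordingly, the sample size of N=100 for the initial phase is not statically based", and no test at that size is scheduled.

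The exact-power shortfall is a separate matter. It exists with m = 1 and adds no weight to the multiplicity point.

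**Conclusion.** The point holds and should be fixed. As written, 9.4.2 leaves the success rule at N=231 at either 2 or fewer events (power 90.4%) or 1 or fewer (power 70.4%), depending on whether the primary is inside the Bonferroni family that the section itself lists. The drop to zero events (33.7%) is conditional on testing more of the Section 3 endpoints. On no reading does the exact test reach the stated 95%; the best is about 90%.

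Assumptions: 231 analysed patients; p0 = .031 applied to the composite; true rate .0047; exact one-sided testing. Section 9.4.4 does not state sidedness, and .0492 is read here as one-sided to match 9.2. The interim look at 50 patients does not change these figures through an early efficacy stop: even zero events gives .969⁵⁰ = .207 against 3.1%, well above .0054.

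**What to change.** In 9.4.2, name one exact one-sided binomial test of the composite (cardiac death or MI) against p0 = .031 as the sole primary test. State that it lies outside the Bonferroni family and is judged at the final-look level in 9.4.4, by cross-reference, under an overall one-sided alpha of .05. Align the wording of 9.1 with this.

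Restrict Bonferroni to a listed secondary family that agrees with Section 3, with m stated and a null rate for each tested outcome. Alternatively, drop those tests and report each outcome as a rate with an exact confidence interval.

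In 9.2, restate power at N=231 as about 90% by exact test, with a success rule of 2 or fewer events.

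The cost is wording only: no added patients, visits or procedures. The stated power becomes less favourable, and each secondary outcome either needs a justified null rate or loses its p-value. The change should be made before outcome data are examined.

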#### 9.4.4 PLANNED INTERIM ANALYSES

A 7 month planned interim analysis for the first 50 patients enrolled using the O'Brien-Fleming method will be conducted for cardiac death or myocardial infarction rate. Using an a priori alpha of .05, the adjusted alpha for the interim analysis will be 0.0054 and 0.0492 for the final analysis for consideration of frequency rates and obtained p-values at each analysis time point. Interim analysis outcomes will be used to assess trial efficacy, early evidence of harm, and safety to inform futility determinations and continuation considerations. Frequency rates on each outcome variable that exceed the non-inferiority margin of  $\pm 5\%$  for the interim analysis will result in temporary halting for further safety evaluations. The project statistician will conduct the planned interim analysis results will be reviewed by the study PI and research team.

---

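### Section 9.4.2 prints the binomial point probability as the test formula; the one-tailed test of 9.1 and 9.2 needs the lower-tail sum, and at N = 231 the two can differ by one event

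*Combined protocol and SAP*

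**What the plan says.** Four places in the combined protocol and SAP bear on the primary test.

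- Section 9.1 sets the alternative as a rate below p0.
- Section 9.2 sizes a "one-sample binomial test with an alpha of .05 (one-tailed), beta of .05", with p0 = .031, an assumed true rate of .0047 and N = 231.
- Section 9.4.2 states: "The binomial test will be conducted to test the significance of deviations from the expected distribution of observations", each observation being classed as an event or no event. "The test formula to be used is as follows" then leads into P(X) = C(n,k) p^k (1-p)^(n-k). The section adds "The a priori alpha level for all statistical tests will be set at .05", gives no side, and applies a Bonferroni correction alpha/m to multiple tests on the same sample without defining m.
- Section 9.4.4 moves the final level to "0.0492 for the final analysis for consideration of frequency rates and obtained p-values at each analysis time point".

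No section writes out a tail sum or a rejection count.

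**The concern.** The printed expression is the binomial mass function. A p-value for p < p0 is that expression summed over 0, 1, ..., k with p set to p0. A single term is never larger than the sum that contains it, so for k of 1 or more, reading the term as the p-value makes a low event count look more significant than it is. The wording about deviations from an expected distribution also fails to carry over the direction fixed in 9.1 and 9.2.

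The benchmark implies 231 × .031 = 7.2 expected events and the assumed rate implies 231 × .0047 = 1.1, so the decision turns on very few events. A difference of one in the allowed count can change the conclusion about the safety of stopping DAPT at one month.

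**Working it through.** **Inputs.** p0 = .031, p1 = .0047, one-sided alpha .05, power .95 and N = 231 (9.2); alternative p < p0 (9.1); final level .0492 (9.4.4); printed formula and undefined m (9.4.2).

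**The plan's own figure.** The arcsine formula is n = ((z_a + z_b)/h)^2, with h = 2·asin(√.031) − 2·asin(√.0047) = .3540 − .1372 = .2168 and z_a = z_b = 1.645. It gives 230.3, rounded up to 231. The stated sample size is therefore reproduced, and it is that of a one-tailed test.

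**Printed formula against lower tail.** For X ~ Binomial(231, .031):

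| Events k | P(X = k), as printed | P(X ≤ k), lower-tail p-value |
|---|---|---|
| 0 | .0007 | .0007 |
| 1 | .0051 | .0058 |
| 2 | .0188 | .0247 |
| 3 | .0460 | .0707 |
| 4 | .0839 | .1546 |

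Worked term: P(X = 3) = C(231,3) × .031^3 × .969^228 = .0460. The tail is .0007 + .0051 + .0188 + .0460, which is .0707 before the terms are rounded.

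**Decision at N = 231, level .05 or .0492.**

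- Printed value read as the p-value: .0460 is below both levels and .0839 is above both. Success would be 3 or fewer events, with one-sided error P(X ≤ 3 | .031) = 7.1%.
- Lower-tail p-value: .0247 passes and .0707 does not. Success is 2 or fewer events, with error P(X ≤ 2 | .031) = 2.5% and power P(X ≤ 2 | .0047) = 90.4%.

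**Dependence on n (unadjusted .0492).** Largest count called significant on the low side:

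| n | Printed formula | Lower tail |
|---|---|---|
| 100 | 0 | 0 |
| 150 | 1 | 0 |
| 180 | 1 | 1 |
| 190 | 2 | 1 |
| 200 | 2 | 1 |
| 210 | 2 | 2 |
| 220 | 2 | 2 |
| 231 | 3 | 2 |

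The gap is intermittent. It is present at the planned 231 and absent at the 100 of the initial phase.

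**Dependence on Bonferroni.** With m = 2 the level is .05/2 = .025 or .0492/2 = .0246. Three events (.0460) then fail even on the printed formula. The correct p-value for 2 events, .02466 to five places, passes .025 but just misses .0246.

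**The case against.** The best defence is that this is an incomplete textbook formula attached to a correctly named test. Section 9.4.2 says a binomial test will be done, 9.1 gives the direction, 9.2 says one-tailed, and 9.4.4 speaks of p-values. Nowhere does the plan say that P(X) itself is compared with alpha, and an analyst running a one-sided binomial test in standard software would get the tail probability. This stands to the extent that the harm is conditional. It does not remove the defect: the text names this expression as the one to use, and a pre-specified test should not depend on the analyst departing from it.

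It is also fair to say that the trial is a pilot meant to generate hypotheses, that only 100 patients are approved for the initial phase, and that the as-treated population may be smaller than the number enrolled. At n = 100 the lower-side rules coincide.

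A reader might go further in two ways that the documents do not support.

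- Used without direction, the formula also flags 11 or more events (P(X = 11) = .0490), for a total null probability of 17.8%. But 11/231 = 4.8% cannot support p < .031, and 9.1 and 9.2 fix the direction.
- A reader might infer three rival success rules of 3, 2 or 1 events by adding a two-sided test. The plan specifies no such test. Moreover, the doubled p-value at 2 events is .0493, which misses .0492 by about .0001 and passes .05.

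**Conclusion.** The formula in 9.4.2 is wrong as written for the test that 9.1 and 9.2 define, and should be corrected. Applied literally at N = 231, it would allow 3 events where the one-tailed exact test allows 2, with a one-sided error of 7.1% instead of the 2.5% of the correct rule (nominal 5%).

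Three conditions must hold together for that figure: the printed value is taken as the p-value, the level is an unadjusted .05 or .0492, and n is one at which the two rules differ. A reader should not infer that the trial's error rate is 7.1% in general. The documents neither say that the formula will be used in that way nor settle m or the number finally analysed. No stated figure is miscalculated; 231 reproduces. That the correct rule has 90.4% power and not the planned 95% is a separate matter, arising because 231 agrees with an approximate formula and not with the exact test.

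**What to change.** In 9.4.2:

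1. Replace the formula with p-value = sum over i = 0 to k of C(n,i) p0^i (1-p0)^(n-i), where p0 = .031, k is the observed number of patients with the primary composite and n is the number actually analysed.
2. State that the primary test is lower one-tailed, as in 9.1 and 9.2, and replace the wording on deviations from an expected distribution with a test that the rate is below p0.
3. State that alpha/m does not apply to the single primary composite test. If it does apply, define m and restate the rule, because .0247 exceeds .0492/2 = .0246.
4. Give a worked example, marked as an illustration at n = 231 and the .0492 final level: 2 events, p = .0247, reject; 3 events, p = .0707, do not reject.

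The cost is one formula and a few sentences, with no change to conduct, data collection or sample size. The only loss is the more lenient 3-event reading. The text should be settled before outcome data are examined.

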## 1 PROTOCOL SUMMARY

### 1.1 SYNOPSIS

Title:	SYNERGY™ Stent System Implantation with mandatory Intra-Vascular Ultra-Sound Guidance to Examine the Safety of Cessation of Dual Anti-Platelet Therapy in High Bleeding Risk Patients One Month (SYNIVUS-DAPT)
Study Description:	This is a prospective multicenter single-arm study designed to characterize the safety of 1 month of dual antiplatelet therapy (DAPT) in a patient population who are at increased risk for bleeding who are undergoing iLab IVUS-guided percutaneous coronary intervention (PCI) with a SYNERGY Everolimus-Eluting Platinum Chromium Coronary Stent System (SYNERGY™ Stent System). We hypothesize that the 1 to 13 month rates of Cardiac Death or Myocardial Infarction (SCAI definition), and Stent thrombosis after Boston Scientific IVUS-guided SYNERGY™ Stents implantation will be low and provide key hypothesis generating information to inform future larger-scale clinical studies
Objectives:	Primary Objectives: To determine the safety of 1-month DAPT in a High Bleeding Risk (HBR) patient population who are undergoing SYNERGY™ stent implantation.
Endpoints:	Primary Endpoint: 

• Rate of cardiac death or myocardial infarction (SCAI definition) from 1 to 13 months post-index procedure in the “as treated” (eligible for 30 day DAPT cessation) population.

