**Study Population:**

Approximately 100 evaluable patients will be enrolled in this study with the possibility to expand enrollment to two hundred thirty one (231).

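### Excluding and replacing patients lost to follow-up, and excluding missing data and an undefined nonadherence, leaves an analysed set that is not ITT and drops events recorded before loss from the binomial test

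*Combined protocol and SAP*

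**What the plan says.** Section 9.3 opens with "The Intention-to-Treat (ITT) Analysis Dataset inclusive of all participants will be included in the analysis". It ends with "Patients lost to follow-up will not be included in planned analyses". Section 9.2 likewise leaves lost patients out of the final analysis and adds that "additional patients will be recruited for study participation to reach the needed sample of 231". Section 9.4.2 goes further: "Missing data, nonadherence and data lost to follow-up will be excluded from the final analysis". Section 9 does not define nonadherence. The nearest definition, in section 7.1, is a DAPT interruption of at least 3 days in the first month. It governs who stops the P2Y12 inhibitor, not who is analysed.

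The synopsis and section 3 name two populations for cardiac death or MI from 1 to 13 months. The primary one carries an *as treated* label followed by a parenthesis that defines it: "eligible for 30 day DAPT cessation) population". The secondary one is the intent-to-treat population, described as all those enrolled. Section 9.4.6 lists any cardiac death, MI or stent thrombosis before 13 months. No section says that an event recorded before loss stays in the test, and none provides for censoring, imputation or a sensitivity analysis.

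On the number 231, the synopsis speaks of about 100 evaluable patients "with the possibility to expand enrollment to two hundred thirty one (231"), and section 9.2 closes by saying that "the total sample size for subsequent phases will remain at 231, inclusive of subjects enrolled on this initial phase".

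**The concern.** An ITT set cannot include all participants and also omit those lost to follow-up. The primary set is settled at the 1-month visit by its eligibility definition, so removing a patient for loss or missing data after that visit changes a set that was already fixed.

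Sections 9.2 and 9.3 remove patients, not just unobserved person-time. A patient who has a non-fatal MI at month 4 and cannot be reached at month 13 therefore takes the MI out of the numerator. This is a single-arm safety study in which 231 × 0.0047 ≈ 1.1 events are expected under the design assumption, so very few patients can decide the result. Replacement restores the sample size but not the population. An undefined nonadherence exclusion also leaves room for decisions made after outcomes are known.

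**Working it through.** **Inputs (section 9.2).** Reference rate p0 = 0.031; assumed rate p1 = 0.0047; one-sided alpha 0.05; power 0.95; N = 231. The documents give no loss rate, so 2% to 15% is assumed below.

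**Step 1: reproduce 231.** Arcsine formula: n = [(z_0.95 + z_0.95) / (2·asin√p0 − 2·asin√p1)]² = (3.290 / 0.2168)² = 230.3, rounded up to 231. The plan's figure reproduces as a number analysed, with no allowance for loss.

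**Step 2: decision rule at 231.** The exact lower tail is P(X ≤ k) = Σ C(231, j) · 0.031^j · 0.969^(231−j), for j = 0 to k.

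| Events | p |
|---|---|
| 0 | 0.0007 |
| 1 | 0.0058 |
| 2 | 0.0247 |
| 3 | 0.0707 |

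At 0.05 with no Bonferroni divisor, success needs at most 2 events. The final alpha of 0.0492 in section 9.4.4 gives the same cutoff.

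**Step 3: put back the excluded patients and one pre-loss MI.** Suppose the plan's analysis shows 2 events in 231. With loss fraction L, the number enrolled is 231 / (1 − L), rounded up. Restoring everyone, with one recorded MI among them and the others having no recorded event, gives 3 events in that larger number.

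| Assumed loss | Enrolled | Left out | p for 3 events | Conclusion at 0.05 |
|---|---|---|---|---|
| 2% | 236 | 5 | 0.064 | reversed |
| 5% | 244 | 13 | 0.054 | reversed |
| 10% | 257 | 26 | 0.041 | unchanged |
| 15% | 272 | 41 | 0.030 | unchanged |

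The denominator grows as well, and 3 events pass from n = 248 (p = 0.0497). At 10% and 15% loss it takes two restored events to reverse the result (4/257, p = 0.098; 4/272, p = 0.074).

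**Step 4: false success under the plan (illustration).** Assume a true overall rate of 3.1%, 10% loss, lost patients at r times the risk of those retained, and none of the lost patients' events counted. The retained rate is 0.031 / (0.90 + 0.10·r), and false success is P(X ≤ 2) at n = 231.

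- r = 1: rate 0.0310, false success 2.5%
- r = 2: rate 0.0282, false success 4.1%
- r = 3: rate 0.0258, false success 6.1%

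**Step 5: limit of these figures.** They apply to 231 analysed. If the eligible set is smaller, the cutoff moves: 2 events give p = 0.0511 at n = 200, which fails.

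**The case against.** Several points on the other side are sound.

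- **As treated.** A reader might infer that excluding nonadherent patients plainly contradicts the primary set. The documents do not support that. The label is compatible with such an exclusion, while the parenthesis fixes the set by eligibility. This is an ambiguity to resolve. First-month non-compliance under section 7.1 already makes a patient ineligible for cessation, so on that reading only the ITT set is affected.
- **One event always decides.** A reader might infer this from the 2-versus-3 boundary. It holds n at 231. Once the excluded patients return to the denominator, it fails at 10% and 15% loss.
- **Narrow harm.** A fatal event ends follow-up, so the recorded events at risk are in practice non-fatal MIs followed by loss of contact. That limits how often it can happen. It does not put the event back in the test.
- **Wording of 9.4.2.** Taken alone, excluding data lost to follow-up could mean only unobserved data. Sections 9.2 and 9.3 exclude patients, which closes that reading.
- **The number 231.** The synopsis refers to evaluable patients and section 9.2 to a total sample size, so the two uses are unclear rather than irreconcilable. Section 7.1 replaces screen failures without saying that only they are replaced.
- **Estimator.** "A time-to-event bivariate exponential distribution function was used to determine criteria for sample sizes" might suggest that a time-to-event primary estimator is needed. For a pilot described as hypothesis-generating, that is a preference. Censoring at last contact does not cure loss related to outcome.

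**Conclusion.** Wrong as written for the ITT set: sections 9.2, 9.3 and 9.4.2 remove patients whom the plan's own definition includes. For the primary set, exclusion for loss or missing data after day 30 conflicts with the eligibility definition, while the effect of later nonadherence is ambiguous. Recorded non-fatal MIs can leave the test.

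Under assumed loss of 2% or 5%, one such event reverses a 2-event success; at 10% or 15% it does not. With 10% loss and lost patients at 2 to 3 times the risk, false success under the plan rises from 2.5% to between 4.1% and 6.1%. Both results assume 231 analysed, alpha 0.05 and no Bonferroni divisor. A reader might infer that the plan is biased towards declaring safety. The documents do not establish this, because the direction depends on who is lost and they give neither a loss rate nor the risk of those lost. The point should be fixed before database lock.

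**What to change.** 1. Delete the exclusion of lost, missing and nonadherent patients in sections 9.2, 9.3 and 9.4.2, and the replacement of lost patients in 9.2.
2. Define ITT as all enrolled patients who received the stent. Define the primary set as those judged eligible for cessation at the 1-month visit, fixed at that visit. Reconcile the *as treated* label with this. Confine any nonadherence exclusion, with a written definition, to a sensitivity analysis.
3. Count every endpoint event recorded up to last contact.
4. Pre-specify a tipping-point analysis for patients with incomplete 13-month follow-up who are event-free at last contact: how many events among them would remove significance. At 231 and 0.05 this is 3, 2 or 1 when 0, 1 or 2 events are observed. A cumulative incidence censored at last contact can be added as supportive; it is not required as the primary estimator.
5. State whether 231 is the number enrolled or analysed.

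The cost is wording changes and one extra analysis. Section 6.4 already requires all stented patients to be followed to 13 months, so no visits are added. Without replacement, slightly fewer patients will have complete follow-up (about 219 of 231 at an assumed 5% loss, 231 × 0.95), and the observed rate may be less favourable.
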